### **b. Inclusion criteria**

#### All phases

1. Age ≥ 18.
2. Able to give written informed consent.
3. Medically and psychiatrically healthy.

4. Enrolled in 01-M-0254 “The Evaluation of Participants with Mood and Anxiety Disorders and Healthy Volunteers” (PI: [name]) or 17-M-0181 “Recruitment and Characterization of Healthy Research Volunteers for NIMH Intramural Studies” (PI: [name]).

#### Additional inclusion criteria for Phase 2

1. Age  $\leq 55$ .
2. Body mass index between 18 kg/m^2 to 32 kg/m^2, inclusive, and body weight of  $\geq 50$  kg (110 pounds).
3. Female subjects must be surgically sterile (bilateral tubal ligation, hysterectomy, or bilateral oophorectomy at least 6 months prior to dosing of BPN14770), at least two years post-menopausal, or willing to use two barrier methods of contraception from initial screening until one month after taking the last dose of study drug.
4. Male subjects must be willing to inform female partners of their participation in the study and must agree to use adequate contraceptive methods (vasectomy performed at least 6 months prior to dosing BPN14770 or use at least one barrier method of birth control).

#### **c. Exclusion criteria –All phases**

##### All phases

1. Clinically significant laboratory abnormalities based on the following tests (performed under screening protocol 01-M-0254 or 17-M-0181): CBC; acute care panel; hepatic panel; mineral panel; urinalysis; urine drug screen; urine pregnancy test (females); and lipid panel; hepatitis panel (A, B, C); syphilis screening test; total protein; uric acid; creatine kinase; cholesterol; thyroid panel; prothrombin and partial prothrombin tests; and EKG.
2. Have a brain disease (such as multiple sclerosis or stroke).
3. Any current Axis I diagnosis, based on interview and self-reporting performed under screening protocol 01-M-0254 or 17-M-0181.
4. Positive HIV test.
5. Current or past history of significant cardiovascular, cerebrovascular, pulmonary, renal, or liver disease. Stable, well-controlled hypertension and hyperlipidemias are allowed.
6. Taking psychotropic drugs (i.e. benzodiazepines or antidepressants) including sedative antihistamines; moderate to strong inhibitors or inducers (i.e. fluconazole or ciprofloxacin) of any CYP450 enzyme. A complete listing of such inhibitors or inducers may be found in Attachment 1, List of P450 inhibitors.
7. Recent exposure to radiation related to research (e.g., PET from other research) that, when combined with this study, would be above the allowable limits.
8. Inability to lie flat on camera bed for at least two hours.
9. Pregnancy or breastfeeding.
10. Positive screen for drugs of abuse or cotinine (at screen or upon admission), or a positive alcohol result (upon admission).
11. Current use of psychiatric medications.
12. NIMH employees and staff or immediate family members of NIMH employee/staff.

#### Additional exclusion criteria for Phase 2 and 4

1. coagulation disorder;

2. thrombocytopenia;
3. Found to have inadequate collateral circulation of the radial artery (see section 5.c screening below)
4. Are unable to have an MRI scan (e.g., pacemakers or other implanted electrical devices, brain stimulators, dental implants, aneurysm clips (metal clips on the wall of a large artery), metallic prostheses (including metal pins and rods, heart valves, and cochlear implants), permanent eyeliner, implanted delivery pumps, or shrapnel fragments, metal fragments in the eye)

Additional exclusion criterial for Phase 2

1. Marked bradycardia (heart rate <45 beats per minute [bpm]) or tachycardia (heart rate >110 bpm) based on supine ECG values obtained at Screening, before the first dose of BPN14770 on the day of the study. Out-of-range vital signs may be repeated once at each eligibility assessment (prior to the start of dosing).
2. History of hematological disorders (e.g., thrombocytopenia) in the immediate family (i.e., parents and siblings).
3. Clinically important or significant conduction abnormalities on single ECG (including QTc interval >450 msec) or evidence or history of long QT syndrome. This exclusion applies to the ECGs obtained at Screening, before the first dose of BPN14770 on the day of the study.
4. Current or past history of gastric or duodenal ulcers or other diseases of the gastrointestinal tract that could interfere with absorption of study drug. Note: Subjects with a history of appendectomy or cholecystectomy may be enrolled.
5. Active acute or chronic infectious diseases.
6. Any history of alcohol or drug abuse within the previous year prior to the Screening visit (per the current edition of the Diagnostic and Statistical Manual of Mental Disorders, 5th Edition: DSM-5), or regular (daily) consumption of alcohol exceeding two bottles of beer, or the equivalent amount of other forms of alcohol (1 serving = 12 oz beer, 5.0 oz wine, or 1.5 oz distilled spirits).
7. Unwilling to abstain from alcohol within 72 hours of before the first dose of BPN14770.
8. Currently ingest nicotine in any way (including smoking cigarettes, vaping, and via patch), or have ingested any nicotine products within the past 3 months.
9. Participation in other clinical studies involving investigational drug within the previous 30 days prior to the first day of the study.
10. Unwilling to forgo donation of blood or blood products (including plasma) during the 8 weeks before the first day of the study.
11. History of allergy to penicillin or sulfonamides, or any other clinically significant drug allergy that includes symptoms such as shortness of breath, rash, or edema.
12. A suicidal ideation intensity score of 2 or higher per screening C-SSRS assessment and/or any suicidal behavior within the past 30 days.

## **4. Study Design and Methods**

### **a. Study overview**

This is a single center study in healthy volunteers. Healthy volunteers will be screened under protocol 01-M-0254 or 17-M-0181. As noted above, participants must meet inclusion and exclusion criteria and sign an informed consent document. The four phases of this study will be:

1) initial first-in-human whole-body imaging of one subject with a low injection activity of 10 mCi;

2) brain imaging at baseline (Scan #1), about 90-180 min after the first dose of BPN14770 (Scan #2), and after three and a half-day administration of BPN14770 (Scan #3) to measure specific binding and  $BP_{ND}$  of  $^{11}\text{C}$ -T-1650 and binding site occupancy of BPN14770. Binding site occupancy in the brain will be compared to plasma levels of BPN14770. The measurement of  $BP_{ND}$  by Lassen occupancy plot [15] assumes no change in PDE4D density after administering BPN14770. Comparison between Scan #1 (baseline) and Scan #2 (90-180 min after the first dose of BPN14770) allows the measurement of  $BP_{ND}$  with little changes in PDE4D density. Comparison between Scan #1 and Scan #3 allows measurement of binding site occupancy by BPN14770 at a steady state level.

3) whole body imaging to estimate radiation-absorbed doses of  $^{11}\text{C}$ -T-1650, and

4) test-retest kinetic brain imaging with arterial blood sampling.

In the past, the NIH Radiation Safety Committee (RSC) required that whole body imaging be performed first in several subjects for any new radioligand to estimate radiation exposure to the body. However, if the radioligand subsequently proved ineffective for brain imaging, then these subjects who underwent whole body imaging would have been unnecessarily exposed to radiation. For this reason, the RSC allowed brain imaging using new  $^{11}\text{C}$ - and  $^{11}\text{F}$ -labeled radioligands to be performed after doing whole body imaging in one subject in order to determine whether the radioligand was worth pursuing as a brain imaging agent. That is, ‘go / no-go’ decisions are made on a small number of subjects based on brain imaging. The request to do so in this protocol follows the identical steps approved for another protocol (14-M-0068, “Evaluation of a Novel Positron Emission Tomography (PET) Radiotracer for TARP  $\gamma$ -8”).

We propose to study up to 40 healthy volunteers: one in Phase 1 (whole body imaging with a low injection activity), 15 in Phase 2 (baseline and blocked brain scans), 9 (whole body imaging to estimate radiation-absorbed doses, and 15 in Phase 4 (test-retest kinetic brain imaging with arterial blood sampling).

To estimate the radiation exposure from this new radioligand, we will follow the prior suggestions from our laboratory [16], which have been approved by the NIH RSC. Specifically, we found that the average exposure of all published human studies with  $^{11}\text{C}$ -radioligands more accurately reflected the exposure to humans than estimation based on imaging in monkeys with that particular radioligand.

Phase 1: One subject will have a first-in-human whole body PET scan with 10 mCi  $^{11}\text{C}$ -T-1650 to confirm that no organ has prominently high uptake of  $^{11}\text{C}$ -T-1650.

Phase 2: 15 healthy subjects will have three brain PET scans, baseline (Scan #1), about 90-180 min after the first dose of BPN14770 (Scan #2), and after three and a half-day administration of BPN14770 (Scan #3). In each scan, 20 mCi of C-T-1650 will be injected. In Scan #1 and #2, the binding will be measured by kinetic brain imaging with arterial blood sampling. In addition, in all of Scan #1, 2, and 3, by using venous samples, radioligand binding will be measured as brain uptake (SUV) normalized to venous concentrations of C-T-1650 because an arterial line will not be placed in Scan #3 due to three-day interval between Scan #2 and 3. Venous samples will be analyzed for BPN14770 levels. The dose of BPN14770 will be 50 mg BID (except for the last day in which subjects will take a single dose).

Phase 3: Nine healthy subjects will have a whole-body scan using 20 mCi of C-T-1650 to estimate radiation-absorbed doses.

Phase 4: 15 healthy subjects will have two brain PET scans; test-retest kinetic brain imaging with arterial blood sampling.

If Phase 2 shows substantial specific (i.e., displaceable) binding, we will be confident that the radioligand itself can be used to measure the density of PDE4D in human subjects, including patients with MDD. For such potential studies, we will need to determine dosimetry and test / retest variability of the PET scans, independent of the results from three-day administration of BPN14770. Thus, if Phase 2 shows substantial (>40%) specific binding in three subjects, we will simultaneously proceed with Phases 2, 3, and 4.

Brain MRI and PET scans are part of the protocol. There will be no brain MRI in the whole body dosimetry studies in Phases 1 and 3. The MRI will be obtained within 12 months of the PET scans (i.e., up to 12 months before or after the PET scan) and can be performed on the same day. Brain PET scans will be performed with vital sign monitoring. In Phase 2 and 4, C-T-1650 brain PET scans will be associated with arterial sampling for the input function measurement except Scan #3 in Phase 2. No arterial input function will be taken for the Phases 1 or 3 studies, however, several venous samples may be obtained in these studies to guide the analysis of arterial samples obtained in the brain scans.

### **Number of visits and time commitment of participants.**

The visits are described below and summarized in Table 5.

#### Phase 1: whole body imaging with 10 mCi injection

1st outpatient visit: pregnancy test; whole body PET (4 hours)

#### Phase 2: brain imaging (20 mCi) at baseline and after BPN14770

1st outpatient visit: pregnancy test; MRI (2 hours)

2nd outpatient visit: pregnancy test; baseline brain PET imaging (4 hours)

3rd outpatient visit: pregnancy test, brain PET imaging starting approximately 90-180 min after the first dose of PDE4D selective inhibitor BPN14770 (6 hours). BPN14770 (50 mg BID) administration will be continued for three and a half days (the last day subjects will take a single dose).

4th outpatient visit: On the last day of BPN administration. The third PET scan will be started about 90-180 min after the last dose of BPN14770 (4 hours)

5th outpatient visit: 3 -7 days after the last dose of BPN14770

The first two brain PET scans may be performed on a single or two different days, based on the availability of the subject and the PET camera. The order of the visits for MRI and PET scans may be changed based on the availability of the scanners. The baseline PET scan and the first PET scan after BPN14770 administration may occur on the same day and, if so, be separated by at least 2.5 hours to allow for decay of the first injection ( $T_{1/2} = 20$  min).

Phase 3: whole body imaging with 10 mCi injection

1st outpatient visit: pregnancy test; whole body PET (4 hours)

Phase 4: test retest kinetic brain imaging (20 mCi)

1st outpatient visit: pregnancy test; MRI (2 hours)

2nd outpatient visit: pregnancy test; brain PET (4 hours)

3rd outpatient visit: pregnancy test; retest brain PET (4 hours)

The PET scans may be performed on one day or on two different days. The order of the visits for MRI and PET scans may be changed based on the availability of the scanners. Both PET scans may occur on the same day and, if so, be separated by at least 2.5 hours to allow for decay of the first injection ( $T_{1/2} = 20$  min).

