### **iii. Design**

- a) Phase 1: We will begin with whole body scanning in a single human subject using up to 10 mCi C-T-1650. The aim of this first scan will be to detect a tracer that disproportionately accumulates in a single radiosensitive organ, such as the gonads. If we confirm that radioactivity is fairly widely distributed in the body, higher activities may be injected.
- b) Phase 2: Fifteen healthy subjects will have three brain PET scans using 20 mCi of C-T-1650. Scan 1 will serve as the baseline scan for comparison to enzyme occupancy studies (Scan 2 and 3). Scans 2 and 3 will be enzyme occupancy studies using the PDE4D selective medication BPN14770. Scans 2 and Scan 3 will be performed approximately 90-180 min after the first dose of BPN14770 and after three-day administration, respectively. Scan 3 will be performed approximately 90-180 min after the last dose of the three-day administration of BPN14770. The dose of BPN14770 is 50 mg BID for three days, and a single dose on the fourth day. Comparison between Scan 1 and 2 provides accurate measurement of nonspecific binding of C-T-1650. Comparison between Scan 1 and 3 provides enzyme occupancy at a stable plasma concentration of BPN14770 based on Phase 1/2 clinical trials performed by Tetra Discovery Partners. Blood samples will be measured for BPN14770 levels.

- c) Phase 3: To obtain dosimetry information, we will perform a whole body PET scan using  $^{11}\text{C-T-1650}$  (20 mCi) in up to nine healthy subjects.
- d) Phase 4: Fifteen healthy subjects will have two brain PET scans using 20 mCi of  $^{11}\text{C-T-1650}$  to study test/retest reproducibility of the PET measurement. BPN14770 will not be administered in Phases 1, 3 or 4.

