#### **BPN14770-CNS-101:**

Twenty-four subjects received BPN14770 (six at each dose level: 5mg/15mg/50mg/100mg) and eight subjects received placebo. Detectable plasma BPN14770 concentrations were measured after dosing starting between 0.5 hour and 1 hour after dosing, continuing through 48 hours after dosing for all four dose levels. Drug absorption was variable but moderately rapid with median  $T_{max}$  values ranging from 1.5 to 3 hours. The plasma pharmacokinetics of BPN14770 after oral administration appeared to be linear for single doses ranging from 5 to 100mg, although a slight trend for a greater than proportional increase in exposure was observed in the 100mg group as compared to the lower dose groups. The apparent terminal elimination half-life of BPN14770 was consistent among dose groups and averaged between 11 and 13 hours.

The following adverse events were reported.

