##### *2) PET Brain Imaging*

After midnight on the day before, participants are not allowed to take caffeine containing drink because caffeine is a nonselective inhibitor of phosphodiesterases. Dedicated brain imaging will be performed using a PET or PET/CT scanner for two to three hours. Participants will be placed on the scanner bed with their head held firmly in place with a thermoplastic mask fixed to the bed. A  $^{68}\text{Ge}$ ,  $^{137}\text{Cs}$ , or CT transmission scan will be performed to measure and correct for attenuation. Tracer infusions will be performed when the subject is already on the scanner bed. After an intravenous bolus of up to 20 mCi, arterial blood samples will be drawn from the arterial catheter during the PET scan. We will collect about 10-20 arterial samples. The sampling will be performed either at discrete time points and/or continuously. In Phase 2, before and after administration of BPN14770, a few samples (< 7) will be obtained to measure concentration of

BPN14770 during each of second and third PET scans. In addition, during each scan of Phase 2, a few venous samples (< 7) will also be obtained to compare venous data of Scan 3 with those in Scan 1 and 2 because it is difficult to place an arterial line with an interval of three days between Scan 2 and 3. Brain uptake (SUV) normalized to venous blood data will be used to compare scan 1 and 3.

The total amount of sampling volume will be about 150 mL in each brain scan. PET images will be acquired in three-dimensional mode with increased length of frame for a total of approximately two to three hours. If the scan lasts more than two hours, the subject will be offered a break out of the camera for approximately 15 minutes. Vital signs (blood pressure, pulse, and respiratory rate) and EKG (either 3- or 12-lead) will be recorded within three hours before tracer injection, and again about 15, 30, and 120 minutes after tracer injection. After the scan, the arterial and venous lines will be removed and the subject will be instructed to void frequently to minimize radiation exposure.

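### Does the 2.5-hour same-day minimum in Phase 2 let BPN14770 into the baseline scan?

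*Combined protocol and SAP*

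**What the plan says.** The Phase 2 visit list in Section 4.a makes same-day scanning optional: "The first two brain PET scans may be performed on a single or two different days". If one day is used, the baseline scan and "the first PET scan after BPN14770 administration may occur on the same day and, if so, be separated by at least 2.5 hours". The reason given is decay of the first injection, with a 20 min half-life. Almost the same sentence appears for Phase 4, where no drug is given.

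Three other timings bear on it:

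- Third Phase 2 visit, same list: "brain PET imaging starting approximately 90-180 min after the first dose of PDE4D selective inhibitor BPN14770 (6 hours").
- Section 4.d, PET Brain Imaging: "Dedicated brain imaging will be performed using a PET or PET/CT scanner for two to three hours".
- Section 1, summary of study CNS-101: "Detectable plasma BPN14770 concentrations were measured after dosing starting between 0.5 hour and 1 hour after dosing". Median Tmax was 1.5 to 3 h.

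On the order of events, the Précis (Design) states: "Scan 1 will serve as the baseline scan for comparison to enzyme occupancy studies (Scan 2 and 3"). The second visit is listed as "baseline brain PET imaging (4 hours"). Table 5 places Scan 1 in Visit 2, and BPN14770 administration together with Scan 2 in Visit 3. No sentence says where the 2.5 h starts and ends, or states for same-day scanning that the first dose comes after the baseline acquisition.

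**The concern.** The 2.5 h figure appears to have been set for tracer decay alone. In Phase 4 that may be all that matters. In Phase 2 a dose must also be given 90-180 min before Scan 2. A 150 min gap is shorter than a scan plus that lead, so the dose seems to land in or before the baseline.

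Scan 1 is the comparator for Scans 2 and 3. Suppose, purely as an assumption, that a constant fraction o1 of sites was already occupied during Scan 1. Apparent occupancy at Scan 2 would then be (o2 − o1)/(1 − o1). With o2 = 50%, it reads 47%, 41% or 33% for o1 = 5%, 15% or 25%, and BP_ND falls by the fraction o1. The decision to open Phases 3 and 4 rests on more than 40% specific binding in three subjects, so a low reading could matter. Time stability of baseline V_T is a primary outcome (Section 9.a), and drug arriving during the scan could disturb it. Only same-day subjects would be affected, and Section 10 does not separate them from the rest.

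**Working it through.** **Inputs.** Floor 150 min, half-life 20 min, injected activity 20 mCi and lead L = 90-180 min (Section 4.a). Scan length D = 120-180 min (Section 4.d). Plasma drug first detectable 30-60 min after dosing (Section 1, CNS-101).

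**The plan's own rationale.** 150/20 = 7.5 half-lives. The fraction left is 2^(−7.5) = 0.0055, or 0.55%, which is 20 × 0.0055 = 0.11 mCi. The floor serves its stated purpose.

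**Where the dose falls at the floor.** The result depends on how the interval is counted.

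- Reading A, injection to injection: the dose is at 150 − L minutes after the baseline injection.
- Reading B, end of Scan 1 to start of Scan 2: the dose is at 150 − L minutes after the end of the baseline scan.

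| Lead (min) | A: dose, from baseline injection | A: drug detectable from scan minute | B: dose, from end of baseline scan | B: drug detectable, from end of scan |
|---|---|---|---|---|
| 90 | +60 | 90 to 120 | +60 | +90 to +120 |
| 120 | +30 | 60 to 90 | +30 | +60 to +90 |
| 150 | 0 | 30 to 60 | 0 | +30 to +60 |
| 180 | −30 | 0 to 30 | −30 | 0 to +30 |

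**Reading A.** The gap between the end of Scan 1 and the second injection is 150 − D: 30 min for a 2 h scan, zero for 2.5 h and −30 min for 3 h. A 3 h baseline cannot be done at the floor at all. For scans that fit (120-150 min), between 120 − 60 = 60 and 150 min of the baseline follow the dose.

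**Reading B.** Overlap is L − 150 when positive, so at most 30 min. Even then drug is first detectable 0-30 min after the scan ends. No combination gives detectable plasma drug before the end of the baseline.

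**What the visit times imply.** The 4 h baseline visit holds the longest scan (3 h). The 6 h visit equals the longest lead plus the longest scan: 180 + 180 = 360 min. The time for the lead is therefore budgeted in the Scan 2 visit. Taken one after the other on the same day, the two visits put the dose after the baseline scan for every lead and scan length. Section 4.d also ties blood sampling for BPN14770 to the second and third scans only, which treats Scan 1 as drug-free.

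**Effect on V_ND.** With constant occupancies, V_T1 = V_ND + V_S(1 − o1) and V_T2 = V_ND + V_S(1 − o2). Hence V_T1 − V_T2 = V_S(o2 − o1) = [(o2 − o1)/(1 − o1)] × (V_T1 − V_ND). The slope of the Lassen plot changes, but the line still crosses zero at V_T1 = V_ND. Under the model used for the bias figures, V_ND, the primary outcome that Section 9.a draws from Scans 1 and 2, is not biased.

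**The case for a change.** The strongest point is that a rule made "be separated by at least 2.5 hours to allow for decay of the first injection" most naturally counts from that injection. Reading B would put injections 120 + 150 = 270 to 180 + 150 = 330 min apart, or 13.5 to 16.5 half-lives, far more than decay needs. The sentence permitting one day sets aside the separate visits without carrying their order over. Taken alone, it could be obeyed with drug already on board at baseline.

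That stands as a comment on the sentence in isolation, but several things weigh against it as a risk:

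- The grammatical subject of the sentence is the scans, not the injections.
- Reading A also fails for the drug-free Phase 4, where a 3 h scan would still be running at the second injection.
- It would have staff give an oral capsule before, or in the middle of, a scan that the protocol calls the baseline throughout, to a subject whose head is fixed in a mask.
- The 2.5 h is a minimum. Longer spacing or separate days satisfies every timing in the protocol.

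The 5%, 15% and 25% figures are not derived from the documents. At a 90 min lead, drug is first detectable only at minute 90-120, so a constant average occupancy is a poor description of what would happen.

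**Conclusion.** The timings are not incompatible. The 150 min floor does not by itself guarantee a drug-free baseline if counted between injections, but the rest of the plan supplies the order: Scan 1 is the baseline, and the first dose belongs to the Scan 2 visit. On the end-to-start reading, the worst case is a dose 30 min before the scan ends, with no detectable plasma drug until the scan is over. Only by reading one sentence apart from the visit list, Table 5 and the meaning of a baseline does one reach a contaminated reference scan.

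This is a gap in wording that a competent PET team fills sensibly, and no change to the plan follows. The conclusion assumes that staff treat dosing as part of the Scan 2 visit, and that the onset of detectable drug in CNS-101 (single doses of 5-100 mg) applies here. The documents support no estimate of bias in occupancy or BP_ND. This review takes no view on what the interval between dose and scan should be.
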